Both Null	12	6.19	8.04	29.8 (8.2, 55.8)	0.006	0.017
One present	32	5.36	5.85	9.2 (-2.3, 22.0)	0.124	
Both present	38	4.71	4.53	-4.0 (-13.3, 6.3)	0.438	

^a 2-sided P values were derived from the mixed models that test PEITC treatment effect on the change of urinary levels of biomarkers within each specific GST genotypes before and after PEITC intake.

^b 2-sided P values were derived from the mixed models that test the interaction term between PEITC intake and GST genotype on the levels of urinary biomarkers.

PROTOCOL TITLE: Watercress in Detoxification of Environmental Toxicants and Carcinogens

VERSION DATE: July 23, 2020

Thus, for SPMA, PEITC caused significant 43.1%, 74.2%, and 95.4% increases in SPMA in the subjects who were *GSTM1* null, *GSTT1* null, and *GSTM1* plus *GSTT1* null, respectively. For the acrolein metabolite 3-HPMA, the corresponding figures were 24.6%, 26.6%, and 32.7%, all statistically significant, while for the crotonaldehyde metabolite HMPMA statistically significant increases of 15.4%, 22.0%, and 29.8% were seen in the *GSTM1* null, *GSTT1* null, and *GSTM1* plus *GSTT1* nulls, respectively. Thus, GST status had a remarkable effect on the ability of PEITC to enhance detoxification of benzene, acrolein, and crotonaldehyde. This was particularly evident for SPMA in the nulls, because these individuals have relatively low basal levels of SPMA, although the increases still did not raise their levels above those of non-nulls. We hypothesize that the significant increases in mercapturic acids observed upon treatment with PEITC is due to induction by PEITC of GSTP1, which is an established catalyst of these reactions, but further studies are required, as induction of GSTP1 by isothiocyanates appears to be complex [65,66]. These studies are beyond the scope of the present proposal, but we will examine this hypothesis in the future, pending the results of the clinical trial proposed here.

Analysis of Watercress for Gluconasturtiin and PEITC

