15.0 Statistical Considerations

Descriptive statistics will be used to summarize subject characteristics, for example subject demographics (age and gender, race, ethnicity, income, current occupation and usual occupation), medical history and current health status for current diagnoses, symptoms and past health problems. Categorical variables will be described by their frequencies and the continuous measurements will be described by their mean, median, range, and standard deviations. We will use paired *t*-test to compare distributions of continuous variables (e.g., age, number of cigarettes per day, number of pack-years of cigarettes smoked over lifetime) between the two treatment groups (watercress and placebo arms). The McNemar's Chi-squared test will be used to compare categorical variables, such as sex, *GSTM1* and *GSTT1* genotypes between the two treatment groups.

The statistical analysis section particularly focuses on Specific Aim 3, which investigates the hypothesis that detoxification of these noxious agents by conjugation with glutathione, as indicated by mercapturic acid levels in urine, will be significantly elevated compared to placebo in subjects who consumed the watercress preparation and are null for *GSTM1*, *GSTT1*, or both. We can test for a Period x Treatment interaction such as testing if the effect of the watercress preparation varies depending on whether it is given in the first period compared to the second period.

PROTOCOL TITLE: Watercress in Detoxification of Environmental Toxicants and

Carcinogens

VERSION DATE: July 23, 2020

We will have baseline measurements on each subject. Participants will be asked to attend clinic visits on days 0 (baseline), 2, 7 and 14 for each of the periods they are receiving product (watercress or placebo). We will compare the baseline measurements on the outcome variables and some important covariates between the two treatment groups through the two-sample t test to see if there is any significant difference between the two groups in order to ensure homogeneous treatment groups. We will also perform repeated data analysis using the measurements on each subject and consider different baseline parameters for the watercress and the placebo group in our multivariate regression analysis described later.

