Measurements: For the comparison between the two treatment groups, we will consider measurements excluding the baseline observation. Measurements will be taken from each subject in the two supplementation sequences as seen in the following diagram:

Group 1: Period #1 (watercress; A1) – washout – Period #2 (placebo; B2)

Group 2: Period #1 (placebo; B1) – washout – Period #2 (watercress A2)

The letter is used to denote supplementation (A for watercress and B for placebo) and the number, 1 or 2, denotes the period. We will assume, in the formulation of statistical models, that the measurements A1, A2, B1, and B2 are “normally distributed” in log-scale. These letters can represent one of our outcome variables: urinary mercapturic acid levels of specific toxicants (e.g. benzene, acrolein, crotonaldehyde, propylene oxide, etc.) or for mercapturic acids generally, or DNA adducts of acrolein.

Main Outcome Variables: Our data analysis will be based on the following “outcome variables”:

$$X1 = B2 - A1; \text{ and } X2 = B1 - A2.$$

This subtraction will cancel the “within-sequence” effects of all subject-specific factors, leaving only two to be modeled and analyzed: the Treatment (or Supplementation) effect and the Period (or Order) effect. The measurements will result in two independent samples. Each will have the same sample size if there are no dropouts or missing data. Otherwise the number of subjects for each group of measurements (i.e., X1 and X2) will differ if there are dropouts and missing data.

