We would obtain values of X1 or X2, which is a log of "ratio" for each subject in each of the two groups with different supplementation order, it's (watercress/placebo) for group 1 and (placebo/watercress) for group 2. We'll then compute the averages of these log ratios, i.e \bar{x}_1 and \bar{x}_2 . We will do this calculation separately for the double null group ($\hat{\alpha}_{nn}$), and single null group ($\hat{\alpha}_{np}$). We will compare this average ratio with the average ratio of the double positive group ($\hat{\alpha}_{pp}$). With the double nulls being about 15% of the population, *GSTM1* single nulls (45%) and *GSTT1* single nulls (23%), we expect to see 60 double nulls, 180 *GSTM1* single nulls, 92 *GSTT1* single nulls, and 68 double positive individuals. If there is no influence of *GSTM1* or *GSTT1*, the effect of watercress supplementation would be the same between the double null and the double positive group or between the single null and the double positive group. We will test for the significance of the genotypic effect by using a two-sample t test.

PROTOCOL TITLE: Watercress in Detoxification of Environmental Toxicants and

Carcinogens

VERSION DATE: July 23, 2020

In order to estimate the power for that comparison, we need information on the variability of mercapturic acid levels within and between subjects. We will compute the variances of each of these genotypic groups separately and then obtain a pooled variance estimate to compute our pooled t test statistic. Based on our previous work, we used an intra-subject CV of 0.4 and an inter-subject CV of 0.6, which translates to a pooled standard deviation of 0.657. According to Table 3, the percentage difference between the Placebo and PEITC groups with the double null genotypes varied from 29.8% to 95.4%, whereas the percentage difference for the double positive genotypes varied from 4% to 7%. In general, we will have 80% power to detect a difference of 35% between the double null and double positive group and given the range of difference between these two groups in Table 3, we expect to have good power to study this interaction between watercress and *GSTM1* or *GSTT1* genotypes.

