Multivariate Regression Analysis: We will use multivariate regression analysis to supplement the t-test by pooling the data together and using each of the primary outcome variables as dependent variable, separately. In addition to the variables representing the supplementation, treatment order, and status of *GST (M1, T1)* genotypes, the list of independent variables will include socio-demographic characteristics such as gender, age, smoker vs non-smoker, baseline smoking level (cigarettes per day), and intake of dietary nutrients. We will fit a linear mixed-effect model where the dependency in the repeated measurements on each individual will be captured through a random effect. The status of *GST (M1, T1)* genotypes will be modeled as fixed-effects and we will test for the null hypothesis of no association between the genotypes and each outcome. Our primary parameter of interest will be the interaction between the treatment order (pre vs post) and the genotype groups (double null, *GSTM1* single null, *GSTT1* single null, and double positives). We will perform a t-test to assess the significance of the interaction parameter. The residual covariance structure should be selected among several candidates, i.e. autoregressive, compound symmetry, unstructured, etc., to estimate the fixed and random effects. We do not anticipate much missing data on the participants. In general, we will assume missingness at random (MAR) and the likelihood-based linear mixed effect model will provide consistent estimates of our parameters of interest in presence of MAR. The models will be assessed through their Akaike's Information Criterion and Bayesian's Information Criterion. The normality of the outcome variables will be assessed and in presence of non-normality, we will also implement Generalized Estimating Equations to study the impact of watercress and genotypes on each outcome variable. We will use the statistical software R packages nlm and gee to perform the above analysis. These packages will also provide the flexibility to fit non-linear mixed effect models to assess the impact of watercress and genotype groups.

PROTOCOL TITLE: Watercress in Detoxification of Environmental Toxicants and Carcinogens

VERSION DATE: July 23, 2020

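### The mixed model's primary parameter is treatment order × genotype, which does not estimate the watercress × genotype effect the trial asks about

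*Combined protocol and SAP*

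**What the plan says.** All of this is in section 15.0 unless stated otherwise.

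- **Question.** Specific Aim 3 holds that mercapturic acid levels "will be significantly elevated compared to placebo in subjects who consumed the watercress preparation and are null for" GSTM1, GSTT1 or both. The genotype comparison then asks whether the watercress effect is the same in double nulls, or single nulls, as in double positives. The power statement refers to that watercress-by-genotype interaction.
- **Role of the mixed model.** "We will use multivariate regression analysis to supplement the t-test by pooling the data together".
- **Its terms.** The list of independent variables begins "In addition to the variables representing the supplementation, treatment order, and status of" GST genotype. Supplementation and order are therefore two different variables.
- **Its primary parameter.** "Our primary parameter of interest will be the interaction between the treatment order (pre vs post) and the genotype groups", to be assessed by a t-test.
- **What order means elsewhere.** Under Main Outcome Variables the plan separates "the Treatment (or Supplementation) effect and the Period (or Order) effect". The genotype paragraph forms log ratios "for each subject in each of the two groups with different supplementation order", which is sequence.
- **The preliminary trial.** Footnote b to Table 3 (section 2.0, Preliminary Studies) says its mixed models "test the interaction term between PEITC intake and GST genotype on the levels of urinary biomarkers".

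**The concern.** The declared primary parameter crosses genotype with order rather than with product. In a two-period crossover these are different contrasts, and by the plan's own usage order means period or sequence. The before/after label in brackets is not defined. It could refer to day 0 against later samples, because the plan also says it will "consider different baseline parameters for the watercress and the placebo group in our multivariate regression analysis described later".

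The t-test remains, so the trial keeps a test of its hypothesis. But the mixed model is the analysis that adjusts for smoking, diet and demographics, and the one whose validity under missing at random the plan invokes, with 15% attrition anticipated in section 10.0. If the sentence is followed, that analysis either carries no information on watercress × genotype or gives a diluted estimate without placebo control. It could then seem to contradict the t-test only because it tests something else. Substituting the right term after seeing the data would look like a post hoc choice.

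**Working it through.** **1. The plan's own figure.** Section 15.0 claims 80% power for a 35% difference, double null against double positive. The inputs are SD 0.657; 60 and 68 participants scaled by 350/400 to 52.5 and 59.5; two-sided 5% (assumed, since no level is stated); and 35% taken as 0.35 on the log scale.

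- SE = 0.657 × √(1/52.5 + 1/59.5) = 0.124
- 0.35/0.124 − 1.96 ≈ 0.85, so power is 0.803

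The figure reproduces, and it belongs to the t-test of watercress × genotype, not to order × genotype.

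**2. What each reading estimates.** For genotype g, let τ_g be the watercress-minus-placebo log difference, π a period effect common to the genotypes, and δ_g any change from day 0 that occurs on placebo too.

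| Reading of the tested term | Contrast within genotype | Difference between genotypes |
|---|---|---|
| Supplementation (intended) | τ_g | τ_nn − τ_pp |
| Period | −τ_g + π in one sequence, +τ_g + π in the other; balanced average π | 0 |
| Sequence | each sequence has one watercress and one placebo period, so τ_g cancels | 0 (without carryover) |
| Day 0 vs on-product, products pooled | τ_g/2 + δ_g | (τ_nn − τ_pp)/2 + (δ_nn − δ_pp) |

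Only the first row is the quantity asked about. With carryover, the sequence row would pick up carryover that differs by genotype, which is still not the watercress effect.

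**3. Size, using Table 3 effects.** Log differences, double null vs double positive:

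- SPMA: ln(1.954/1.061) = 0.611
- HMPMA: ln(1.298/0.960) = 0.302
- 3-HPMA: ln(1.327/1.070) = 0.215

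Assumptions: watercress acts as PEITC did; 52 vs 60 participants; within-person log SD √ln(1 + 0.4²) = 0.385 and between-person √ln(1 + 0.6²) = 0.555, from the plan's CVs; three independent on-product samples and one day 0 sample per period; no period effect or carryover.

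Closed form for 3-HPMA:

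- Intended: variance per person 2 × 0.148/3 = 0.099; SE = √(0.099 × (1/52 + 1/60)) = 0.060; power about 95%.
- Before/after: variance per person 0.148/6 + 0.148/2 = 0.099, so the same SE of 0.060, but the effect is 0.215/2 = 0.108; power about 44%.

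Simulated rejection rates (3,000 replicates; ranges cover visit-level and period-mean models, with sequence allocated at random or balanced within genotype):

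| Outcome | Supplementation × genotype | Before/after × genotype |
|---|---|---|
| SPMA | 100% | 99.8% |
| HMPMA | 99.9% | 69–71% |
| 3-HPMA | 94–96% | 42–43% |

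For these outcomes sequence × genotype rejected in 4.3–5.4% and period × genotype in 0.6–5.0%, with mean estimates of about 0.00. With equal effects in both genotypes, all tests rejected in 4.6–5.3%.

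**4. Different inputs.** With 60 vs 68 participants, one on-product measurement per period, a period effect of 0.1 and a true difference of ln(1.35) = 0.300 (4,000 replicates), the mean estimates and rejection rates were:

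- supplementation × genotype: 0.300, 87%
- period × genotype: 0.000, 5.5%
- sequence × genotype: 0.002, 5.6%
- before/after × genotype: 0.152, 60%

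**The case against.** The best defence is that this is a slip of wording. Table 3's footnotes describe the PEITC effect both as a change before and after intake and as an intake-by-genotype interaction, although the table's columns are placebo and PEITC. The before/after label may be the same shorthand, so the intended term may be the right one. The paragraph's later, general statements of aim point that way. This is plausible, but those statements specify no interaction term, and treatment order is listed beside supplementation as a different variable. The sentence needs correcting on any view.

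The pooled before/after reading is also the least supported. The plan says the treatment comparison excludes the baseline observation, and separate baseline parameters by product suggest that products would be kept apart. That is fair, but it pushes the sentence back to the period or sequence reading, where the estimate is zero.

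The consequences are limited too. The model is supplementary, stable covariates largely drop out of a within-person contrast, and the plan expects little missing data. This lowers the stakes without removing them.

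Finally, the percentages depend on treating the three on-product samples as independent. If they carry the information of one, 3-HPMA power is about 55% for the intended term and 31% for before/after; at SD 0.657 the intended term has about 41%. This stands, and the percentages should be read as illustrations. The zero expectation and the halving are algebra and do not depend on it.

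**Conclusion.** The concern holds. As written, the mixed model's primary parameter does not estimate the watercress × genotype effect under the period, sequence or pooled before/after reading. It has expectation zero if order is period or sequence, given balanced sequences and no period or carryover effect that differs by genotype. It is half the intended effect, without placebo control, if it is a pooled before/after contrast; for 3-HPMA that is a ratio of 1.11 instead of 1.24. The power figures also assume that watercress effects equal the PEITC effects in Table 3.

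The defect is limited to the supplementary model, is probably a drafting error, and leaves the t-test and its power statement intact. It should still be corrected before the data are analysed.

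**What to change.** Replace the sentence with: *The primary parameter of the mixed model is the supplementation (watercress vs placebo) × genotype-group interaction, with period and sequence as fixed adjustment terms.* Delete or define the before/after label. If day 0 samples enter the model, define them as the period-specific baseline, not as one level of the tested term.

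It would also help to report the watercress/placebo ratio within each genotype group from the same model. The interaction answers whether the effect differs by genotype; the ratios within the null groups answer Specific Aim 3 as worded.

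The essential correction is one sentence, and the baseline definition and the ratios add a line or two. No new data are needed and trial conduct does not change.

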16.0 Confidentiality

All investigators and staff associated with this project have been trained, and new hires will be trained, on human research ethics and Good Clinical Practice in accordance with the requirements of the University of Minnesota.

Only the immediate study team (Project Manager, Study Coordinator and Principal Investigators) will have access to individually identifiable private information about participants. Coded ID's will be used throughout the study by all the researchers involved. Original signed consent forms and other identifiable information will be kept separate from the research information in a secure and locked space/database.

17.0 Provisions to Monitor the Data to Ensure the Safety of Participants

Oversight for quality control and adherence to protocol procedures will be conducted by the Project Manager in collaboration with the co-Principal Investigators. A start-up meeting with the whole research team will take place prior to participant enrollment. During this meeting, there will be training on the study protocol, standard operating procedures, equipment and data collection platforms. The co-Principal Investigator, [name], will closely monitor the research staff on the procedures to be used in this study. Such monitoring will consist of frequent in-person discussion of study visits and other procedures to make sure that all protocol procedures are followed, and

PROTOCOL TITLE: Watercress in Detoxification of Environmental Toxicants and Carcinogens

VERSION DATE: July 23, 2020

regular research team meetings to provide updates on study progress and review the data collection process, the results from data monitoring and other issues of concern.

Standard operating procedures will be developed for consistent implementation of the protocol. The Study Coordinator will be administering all measures during clinic visits and entering the information about each subject into a database. Each visit will have a checklist of all measures that need to be obtained and the order by which they will be administered. The Project Manager will be directly supervising the Study Coordinator and will periodically review protocol compliance and implementation, and adherence to good clinical practice procedures.

The Study Coordinator will go over the questionnaire instructions and will be available to the participant to answer any questions he/she may have. Questionnaires will be reviewed for completeness, however, they may choose not to answer questions.

Once a participant has completed all study procedures and all open events have been closed, the PI will review the participant's binder and sign a form indicating study completion for that participant.

This is a minimal risk, non-therapeutic study. While participating in the trial, AEs and concomitant medications will be assessed at every study visit and vital signs will be obtained periodically. The Co-Principal Investigator, [name] will meet regularly with the study staff to review recruitment progress and any adverse events. Entrance criteria will be reviewed following screening. Study participants will be under medical supervision while in the study and our research staff will make appropriate referrals to the physician should any adverse events occur. The Data Safety Monitoring Board (DSMB) and other regulatory bodies will be informed of any adverse events either at the regularly convened meetings or in the annual report, or if necessary, immediately.

The DSMB, potentially comprised of a biostatistician, clinical research scientist (MD) and medicinal chemist, will begin by reviewing the protocol and establishing guidelines for data and safety monitoring. This will include developing standard procedures for day-to-day monitoring by the internal monitors, investigators and study staff. This Board will meet at regular intervals (at least once a year) to evaluate the progress of the trial, review data quality, patient recruitment, study retention, and examine other factors that may affect study outcome. They will also review the participant's ability to achieve the study requirements and the rates of adverse events to determine whether there has been any change in participant risk. Their review will ensure that subject risk does not outweigh the study benefits. A brief report will be generated from each of these meetings for the study record and forwarded to the Institutional Review Boards (IRB).

The DSMB will be available to convene outside of the regular meetings, if necessary, if concerns should arise regarding a particular subject, or any troublesome trends in the subject experiences. They will make appropriate recommendations for changes in protocol, if needed.

AEs will typically be identified during the administration of the Health Changes Questionnaire. Other events may be identified from physiological study measures or by spontaneous reports during assessments.

PROTOCOL TITLE: Watercress in Detoxification of Environmental Toxicants and Carcinogens

VERSION DATE: July 23, 2020

Assessment of Questionnaire Items

- Health Changes Questionnaire: If the participant answers 'YES' to Questions 1, 2, or 3, the interviewer will assess for an 'Adverse Event.'
 - 1) *Have you had any negative changes in your health since your last visit?*
 - 2) *Have you had any changes in medication since your last visit?*
 - 3) *Since your last visit, have you received any form of medical care?*

Assessment of Physiological Data

- Blood Pressure:
 - The 'Adverse Event Log' and 'Blood Pressure and Heart Rate Symptom Checklist' will be completed if an automatic and subsequent manual blood pressure measurement during the same visit is at or above 160 systolic or 100 diastolic.
 - The 'Adverse Event Log' and 'Blood Pressure and Heart Rate Symptom Checklist' will be completed if an automatic and subsequent manual blood pressure measurement during the same visit is below 90 systolic or 50 diastolic and the participant is experiencing symptoms listed on the 'Blood Pressure and Heart Rate Symptom Checklist.'
- Heart Rate:
 - The 'Adverse Event Log' and 'Blood Pressure and Heart Rate Symptom Checklist' will be completed if an automatic and subsequent manual heart rate measurement during the same visit is at or above 105 bpm.
 - The 'Adverse Event Log' and 'Blood Pressure and Heart Rate Symptom Checklist' will be completed if an automatic and subsequent manual heart rate measurement during the same visit is below 45 bpm and the participant is experiencing symptoms listed on the 'Blood Pressure and Heart Rate Symptom Checklist.'

Adverse Events Communicated by Participants

The occurrence of AEs will be sought by non-directive questioning of the participant at each visit during the study. AEs also may be detected when the participant volunteers them during or between visits or through physical examination, laboratory test, or other assessments.

Review and Reporting of Adverse Events and Serious Adverse Events

Co-Principal Investigators with oversight from [name]. (Medical Monitor) and the clinic's licensed medical professional will review all AEs and assess whether they are related to the study product.

An AE is defined as the appearance or worsening of any undesirable sign, symptom, or medical condition occurring after starting the study procedures even if the event is not considered to be related to the study product. Medical conditions/diseases present before starting the study are only considered adverse events if they worsen after starting the study product. Abnormal laboratory values or test results constitute adverse events only if they induce clinical signs or symptoms, are considered clinically significant, or require therapy; there are no plans for active monitoring of laboratory tests as part of this project.

PROTOCOL TITLE: Watercress in Detoxification of Environmental Toxicants and Carcinogens

VERSION DATE: July 23, 2020

To the extent possible, each adverse event will be evaluated to determine:

1. the severity grade (mild, moderate, severe)
2. its relationship to the study product used (suspected/not suspected)
3. its duration (start and end dates or if continuing at final exam)
4. outcome (resolved/improved/unchanged/worsened; study product temporarily interrupted or permanently discontinued due to this adverse event; concomitant medication taken; non-drug therapy administered)
5. whether it constitutes a SAE

Information about all SAEs will be collected and recorded on the project's Serious Adverse Event Report Form. A SAE is defined an undesirable sign, symptom or medical condition which:

1. is fatal or life-threatening;
2. requires or prolongs hospitalization;
3. results in persistent or significant disability/incapacity;
4. constitutes a congenital anomaly or a birth defect;
5. is medically significant, in that it may jeopardize the subject and may require medical or surgical intervention to prevent one of the outcomes listed above.

Events not considered to be SAEs are hospitalizations that are:

1. elective or pre-planned, for a pre-existing condition that is unrelated to the products under study and did not worsen;
2. for general care, and/or overnight observation;
3. treatment on an emergency, outpatient basis for an event not fulfilling any of the definitions of serious given above and not resulting in hospital admission.

Safety evaluation will be performed on all accrued participants for whom study products were dispensed. The assessment of safety will be based on the frequency of AEs and severity grade of AEs. Other safety data (e.g. vital signs) will be considered as appropriate.

Any SAE occurring after the participant has signed the consent form and until the last encounter with the participant will be reported. All AEs will be summarized by presenting, for each treatment group, the number and percentage of participants who experienced any AE, the number reporting AEs in each body system and the number of AEs by type. Any other information collected (e.g., severity or relatedness to study product) will be listed as appropriate. A summary of clinically relevant toxic events, such as AEs leading to death or rated as SAEs, those with a suspected relationship to study product, or AEs requiring further medication or non-drug therapies will be provided. Reports will be reviewed regularly by the study investigators.

